#### 9.1.1.1 BMI (COMPARED TO PREVIOUS ASSESSMENT)

	
 
Moderate decrease in the direction of the normal range [<25 kg/ m2] b at least 5 BMI units
 
	-
	
 
Minor decrease in the direction of the normal range [<25 kg/ m2] by more than 2 but less than 5 BMI units
 
	1
	
 
No significant change (BMI remains within +/- 2 BMI units compared with start) OR BMI remains <25 kg/ m2
 
	1
	
 
Minor increase in BMI (increase by more than 2 but less than 5 BMI units, to above the upper limit of normal BMI [≥25kg/m2])
 
	l
	
 
Moderate increase in BMI (increase by at least 5 BMI units above normal BMI [≥25kg/m2])
 
36
 
	6
9.1.1.2	Glucose tolerance (compared to previous assessment)	
	• Moderate improvement in glucose tolerance: -4	4
	• HbA1c declined >10% from start AND medication decrease	
	• Minor improvement in glucose tolerance: -3	2
	
 
O HbA1c declined >10% from start AND no medication increase (unchanged or missing) AND start HbA1c ≥ 5.7
 
	e
	• HbA1c within 10% of start AND decrease in diabetic medicate	ion
	
 
HbA1c < 5.7 AND decrease in diabetic medication AND HbA increased >10%
 
	.1c
	• No significant change in glucose tolerance: 0	
	
 
HbA1c within 10% of start or (start and follow-up) HbA1c < 5 AND no change in medication (or missing)
 
	5.7
	• HbA1c increased > 10% of start AND a decrease in medicatio AND follow-up HbA1c $\ge 5.7$	n
	
 
HbA1c decreased by > 10% of start AND an increase in medication
 
	
	• Minor worsening of glucose tolerance or medication status: 3	2
	• HbA1c increased >10% of start AND no change in medication (or missing) AND follow-up HbA1c $\geq$ 5.7%	1
	
 
HbA1c within 10% of start AND increase in diabetic medicati
 
	on
	• Moderate worsening of glucose tolerance despite increased diabetic	4
	treatment: 4	4
	• HbA1c increased >10% of start AND an increase in diabetic medication AND follow-up HbA1c $\geq 5.7\%$	

Note: changes in medication for glucose control, used in the above weight derivations, are assessed as a GTI specific question.

SGS	Statistical Analysis Plan	
ARGX-113-1905	Final analysis	Final 1.0 of 26APR2024

#### 9.1.1.3 **BLOOD PRESSURE (COMPARED TO PREVIOUS ASSESSMENT)**

- Moderate improvement in BP: • • Decrease in either systolic or diastolic BP of >10% of start AND medication decrease AND start systolic BP  $\geq$ 120 mmHg or start diastolic BP  $\geq$  85 mmHg Minor improvement in BP: • Decrease in either systolic or diastolic BP of >10% of start AND no medication increase (unchanged or missing) AND start systolic BP  $\geq$ 120 mmHg or start diastolic BP  $\geq$  85 mmHg • Systolic AND diastolic BP within 10% of start AND a decrease in medication  $\circ$  Systolic BP < 120 and diastolic BP < 85 (both start and end) AND a decrease in medication No significant change in BP: • Systolic AND diastolic BP within 10% of start or (start and follow-up) systolic / diastolic BP < 120/85 resp AND no change in medication (or missing)  $\circ$  Increase in systolic or diastolic BP >10% of start AND a decrease in medication AND follow-up systolic BP ≥120 mmHg or diastolic BP  $\ge 85 \text{ mmHg}$  $\circ$  Decrease in systolic or diastolic BP of > 10% of start AND an increase in medication AND start systolic BP  $\geq$ 120 mmHg or diastolic BP  $\geq$  85 mmHg Minor worsening of BP:
  - $\circ$  Increase in systolic or diastolic BP >10% of start AND no change in medication (or missing) AND follow-up systolic BP  $\geq$ 120 mmHg or diastolic BP  $\geq$  85 mmHg
  - o Systolic AND diastolic BP within 10% of start AND an increase in medication
  - $\circ$  Systolic BP < 120 and diastolic BP < 85 (both start and end) AND an increase in medication
- Moderate worsening of BP despite treatment
  - $\circ$  Increase in systolic or diastolic BP >10% of start AND an increase in medication AND follow-up systolic BP ≥120 mmHg or diastolic BP  $\ge 85 \text{ mmHg}$

#### Notes:

1. changes in medication for BP control, used in the above weight derivations, are assessed as a GTI specific question.

2. check  $\geq$  normal range and > 10% needs to be done separately for systolic and diastolic BP. In case of both an increase and decrease occurs, this is considered as no change in BP and the score will be based on the change in medication (score = +/-19for increase/decrease, score = 0 for no change).

-44

-19

0

19

44

SGS	Statistical Analysis Plan	
ARGX-113-1905	Final analysis	Final 1.0 of 26APR2024

3. Hypertensive Emergency = Y or PRES = Y at current visit is provided a score 44 regardless of the value at previous visit

#### 9.1.1.4 LIPID METABOLISM (LDL COMPARED TO PREVIOUS ASSESSMENT)

- Moderate improvement in lipids:
   -30

   o
   Decrease in LDL concentration >10% of start AND medication decrease
- Minor improvement in lipids: -10
  - Decrease in LDL concentration >10% of start AND no change in medication (or missing) AND start above target range
  - o LDL within 10% of start AND decrease in medication
- No significant change in lipids:

•

- LDL within 10% of start AND no change in medication (or missing)
- $\circ$  Increase in LDL > 10% of start AND decrease in medication
- Decrease in LDL > 10% of start AND no medication change (or missing) AND start LDL below or equal target range
- $\circ$  Decrease in LDL > 10% of start AND increase in medication
- Minor worsening of LDL or medication status: 10
  - Increase in LDL >10% of start AND no change in medication (or missing)
  - LDL within 10% of start of start AND increase in medication
- Worsening of LDL despite treatment: 30

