10.12. Appendix 12: Glucocorticoid Toxicity Index (GTI)

Table 10:Approach to Calculating the Baseline GTI 2.0 Score: Toxicities Assigned
Weighted Scores from the C-GTI to Establish a Baseline GTI Score

Toxicity domain		Points
Body mass index (BMI)	BMI < 27	0
	$BMI \ge 27 \text{ but} < 30$	21
	$BMI \ge 30$	36
Glucose metabolism	HgbA1c < 5.7	0
	HgbA1c < 5.7 but on medication	32
	HgbA1c ≥ 5.7	32
	HgbA1c ≥ 5.7 and on medication	44
	Diabetic retinopathy, nephropathy, or neuropathy (count only one)	44
Blood pressure	Normotensive: systolic ≤ 120 and diastolic ≤ 85 no medications	0
-	Systolic ≤ 120 and diastolic ≤ 85 but on medications	19
	Systolic > 120 or diastolic > 85 on no medications	19
	Systolic > 120 or diastolic > 85 and on medications	44
	Hypertensive emergency or PRES (count only one)	44
Lipid metabolism	$LDL \leq target$	0
	$LDL \leq target but on medications$	10
	LDL > target on no medications	10
	LDL > target on treatment	30
Bone/tendon	Normal BMD or no known history of osteoporosis	0
	Osteoporosis	29
	Insufficiency fracture secondary to osteoporosis	29
	Osteonecrosis	29
	Tendon rupture while on corticosteroid	29
Glucocorticoid myopathy	No myopathy	0
1.5	Minor glucocorticoid myopathy	9
	Moderate glucocorticoid myopathy	63
	Severe glucocorticoid myopathy	63
Skin	No skin toxicity	0
	*Minor skin toxicity (1 or more than 1 minor skin item)	8
	*Moderate skin toxicity (1 or more than 1 moderate skin item)	26
	*Severe skin toxicity (1 or more than 1 moderate skin item)	26
	*Select only 1 (minor, moderate, or severe)	
Neuropsychiatric	No neuropsychiatric toxicity	0
	*Minor (1 or more than 1 minor NP item: insomnia, mania, depression, cognitive)	11
	*Moderate (1 or more than 1 moderate NP item: insomnia, mania, depression, cognitive)	74
	*Severe (1 or more than 1 severe NP item: insomnia, mania, depression, cognitive)	74
	Psychosis	74
	Glucocorticoid-induced violence	74
	*Select only 1 (minor, moderate, or severe)	
Infection	No GTI-relevant infections within the prebaseline GTI interval of the study	0
	Oral or vaginal candidiasis or noncomplicated zoster (<grade 3)="" gti="" interval="" of="" prebaseline="" study<="" td="" the="" within="">19	</grade>	19
	Grade 3 or grade 4 infection within the pre-baseline GTI interval of the study	93
Ocular	Increased IOP	33
	Posterior subcapsular cataract	33
	Central serous retinopathy	33
Gastrointestinal	GI perf absence of NSAIDs	33
	PUD without Helicobacter pylori	33
Endocrine	Adrenal insufficiency	33

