## $\circ$ Increase in LDL >10% of start AND an increase in medication

Notes: 1. changes in medication for lipid control, used in the above weight

derivations, are assessed as a GTI specific question.

2. target range for LDL is 1.81mmol/L

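### With lipid medication unchanged, the C-GTI lipid rule applies the LDL target to falls but not to rises, so a rise that stays within target scores +10 and its reversal scores 0

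*SAP*

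**What the plan says.** SAP Appendix 9.1.1.4 scores LDL at each GTI assessment against the previous one. Where lipid medication is unchanged or its status is missing, three rules govern a change of more than 10%:

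- A rise scores +10: "Increase in LDL >10% of start AND no change in medication (or missing"). No target is mentioned.
- A fall scores -10 only under the condition "medication (or missing) AND start above target range".
- A fall scores 0 in the remaining case: "Decrease in LDL > 10% of start AND no medication change (or missing) AND start LDL below or equal target range".

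The notes to the section fix the threshold: "target range for LDL is 1.81mmol/L".

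Where medication changes, a rise with more medication scores +30 ("Increase in LDL >10% of start AND an increase in medication"), a fall with less medication scores -30, and neither rule refers to the target. A rise with less medication is listed under no significant change ("LDL > 10% of start AND decrease in medication").

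Under SAP 9.1.2, CWS adds up positive weights only, and AIS adds up positive and negative weights. Protocol 8.3.10 describes AIS as giving a negative score when a toxicity that was present at baseline or arose during the trial resolves.

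**The concern.** The target enters the unchanged-medication rules on one side only. A participant whose LDL moves about below 1.81 mmol/L collects worsening points on the way up and nothing on the way down. This sits badly with the protocol's account of AIS, because the recorded worsening resolves with no offsetting negative score.

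It also departs from the neighbouring domains. The blood pressure worsening rule asks for an abnormal follow-up value ("Increase in systolic or diastolic BP >10% of start AND no change in medication (or missing) AND follow-up systolic BP" at or above 120 mmHg, or diastolic at or above 85). The glucose rule asks for follow-up HbA1c of at least 5.7. The BMI rule gives 0 while BMI remains below 25. With unchanged medication, lipids is the only one of these four domains in which movement wholly inside the normal range counts as glucocorticoid toxicity.

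C-GTI, reported as CWS and AIS, is the endpoint for the secondary objective on the health impact of glucocorticoids. The error always points towards toxicity.

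**Working it through.** The plan gives no figure to reproduce here, so the rule was applied as written.

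**Inputs.** Target 1.81 mmol/L and weights +10, -10 and 0 (SAP 9.1.1.4 and its notes); CWS and AIS summation (SAP 9.1.2); GTI at roll-over, Week 26 and Week 52, hence two intervals. Percent change = 100 × (follow-up − start) / start. Medication is unchanged throughout.

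**Worked patterns**

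| LDL, mmol/L | Interval 1 | Interval 2 | AIS | CWS |
|---|---|---|---|---|
| 1.40, 1.60, 1.40 (within target) | +14.3%: +10 | -12.5%: 0 | +10 | +10 |
| 3.00, 3.42, 3.00 (above target) | +14.0%: +10 | -12.3%: -10 | 0 | +10 |
| 1.70, 2.10, 1.70 (across target) | +23.5%: +10 | -19.0%: -10 | 0 | +10 |
| 1.20, 1.40, 1.60 (within target) | +16.7%: +10 | +14.3%: +10 | +20 | +20 |

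The rule is symmetric above and across target, so the fault lies only within target. If +10 also requires follow-up LDL above 1.81, the first and last rows become 0 on both scores and the other two do not change.

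**The 30-point pair.** 1.40 to 1.60 with a medication increase scores +30, and 1.60 to 1.40 with a medication decrease scores -30. This pair is balanced.

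**Comparison with the protocol.** Table 11 of Appendix 12, which governs change scores, gives 10 for an increase in LDL or in medication and -10 for a decrease in either, with no target on either side. The SAP added a target to the improvement side only. SAP 6.1 does not list this as a change. It does not list the thresholds that the SAP added for HbA1c and blood pressure either, but those were added on both sides of the unchanged-medication rules.

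**Average size.** The documents give no LDL distribution, so this part rests on assumptions: no true LDL change, unchanged medication, lognormal within-person variation with CV 8% or 12%, and 1,000,000 simulated participants over two intervals.

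- Usual LDL 1.2 to 1.6 mmol/L: mean AIS is 3.1 to 5.7 as written and 0.0 to 0.1 with the added condition; mean CWS is 4.0 to 5.7 as written and 0.0 to 2.3 with it.
- Usual LDL 2.0 to 3.0 mmol/L: mean AIS is 0.4 to 0.5 either way, a residue of measuring change as a percentage of the start value. CWS changes by less than 0.1.
- Assumed populations with mean 2.2, 2.7 or 3.2 and between-person SD 0.6 or 0.9 mmol/L (0.3% to 39% at or below target at baseline): the excess is about 0 to 1.7 points per participant on each score. The largest case is AIS 1.95 − 0.26 = 1.69 and CWS 5.73 − 4.04 = 1.69.

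**The case against.** The strongest reply is that the +10 rule agrees with Protocol Table 11, and that the target condition on falls is the SAP's own addition. Deleting that condition would also restore symmetry in AIS and would stay closer to the table. GTI 2.0 is an external instrument, and its published lipid rule cannot be read from these documents. This stands as a reason to check the source before editing. It does not rescue the rule as written, because neither Table 11 nor the neighbouring domains support a one-sided target with unchanged medication.

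Four stronger readings are tempting, and the documents do not support them.

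- A reader might infer that every LDL rise above 10% counts as worsening. It does not: with a medication decrease it scores 0.
- A reader might infer that the +30 rule has the same fault. The -30 rule is equally free of any target. Restricting +30 alone, and scoring the within-target case +10, would set +10 against -30 and create an imbalance towards improvement. The glucose domain has an imbalance of that kind: its -44 rule has no start-value condition, while +44 needs follow-up HbA1c of at least 5.7.
- A reader might infer that the mismatch between rises and falls makes CWS drift. Falls never enter CWS, and by design it also keeps +10 in the above-target example. The only question for CWS is whether within-target rises should count at all.
- A reader might take Protocol Table 10, where 10 points go to "LDL > target on no medications" and none to LDL at or below target without medication, as proof that the change score should be 0. Table 10 sets the baseline score; change scores come from Table 11.

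**Conclusion.** The point holds for unchanged or missing lipid medication. AIS is asymmetric within target, and CWS counts rises within target that the BMI, HbA1c and blood pressure rules would score as 0.

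The error is real but small. It is at most +10 per interval and +20 over two, and it is confined to participants at or below 1.81 mmol/L at follow-up. The averages above depend entirely on the assumed LDL distribution and within-person variation. For scale, a single infection item can carry 93 points.

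C-GTI is summarised descriptively, no hypothesis is tested, comparisons between prior treatment groups are descriptive, and the C-GTI table is not marked as a topline output. No test, sample size or decision rule is affected, so a reader should not infer that the trial's conclusions are at risk.

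**What to change.** After checking against the GTI 2.0 scoring source, amend SAP 9.1.1.4 as follows:

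1. Add *AND follow-up LDL above target range* to the +10 rule for a rise above 10% with medication unchanged or missing.
2. Under no significant change (0), list a rise above 10% with follow-up LDL at or below target and medication unchanged or missing.
3. Leave the +30 and -30 rules as they are, or add a target condition to both together.
4. Record the LDL target conditions in SAP 6.1 as a departure from Protocol Table 11.

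Removing the start-above-target condition from falls is the alternative. It would cure the AIS asymmetry and match Table 11, but CWS would go on counting rises within target, so the first option is preferable unless the instrument says otherwise.

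The cost is a few lines of SAP text and one programming condition. No new data are needed.

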## $\circ$ Increase in LDL >10% of start AND an increase in medication

Notes: 1. changes in medication for lipid control, used in the above weight

derivations, are assessed as a GTI specific question.

2. target range for LDL is 1.81mmol/L

## 9.1.1.5 *Glucocorticoid-induced myopathy (compared to previous assessment)*

٠	Moderate/severe weakness to none:	-63
•	Moderate/severe weakness to mild weakness:	-54
•	Mild weakness to none:	-9
•	No significant change:	0
•	None to mild weakness:	9
•	Mild to Moderate/severe weakness:	54
٠	None to Moderate/severe weakness:	63

0

SGS	Statistical Analysis Plan	
ARGX-113-1905	Final analysis	Final 1.0 of 26APR2024

#### 9.1.1.6 Skin toxicity (compared to previous assessment)

Allocate weights for each of the 5 subitems : acneiform rash, easy bruising, hirsutism, atrophy/striae, erosions/tears/ulcerations

• Moderate/severe to none:	-26
• Moderate/severe to minor:	-18
• Minor to none:	-8
• No significant change:	0
• None to minor:	8
• minor to moderate/severe:	18
• None to moderate/severe:	26

Note: minor and mild or used fully interchangeable.

For the derivation from the grading to severe, moderate, minor (or mild): see table underneath:

Minor/Mild	Moderate	Severe (Specific Domain)
Acneiform rash (Grades 1- 2)	Acneiform rash (Grade 3)	Acneiform rash (Grade 4)
Easy bruising (Grade 1)	Easy bruising (Grade 2)	
Hirsutism (Grade 1)	Hirsutism (Grade 2)	
Atrophy/Striae (Grade 1)	Atrophy/Striae (Grade 2)	Atrophy/Striae (Grade 3)
Erosions/Tears/Ulcerations (Grade 1)	Erosions/Tears/Ulcerations (Grade 2)	Erosions/Tears/Ulcerations (Grade 3)

SGS	Statistical Analysis Plan	
ARGX-113-1905	Final analysis	Final 1.0 of 26APR2024

#### 9.1.1.8 NEUROPSYCHIATRIC EFFECTS (COMPARED TO PREVIOUS ASSESSMENT)

Allocate weights for each of the 4 subitems : insomnia, mania, cognitive impairment, depression

• Moderate/severe to none:	-74
• Moderate/severe to minor:	-63
• Minor to none:	-11
• No significant change:	0
• None to minor:	11
• Minor to moderate/severe:	63
• None to moderate/severe:	74

#### Notes:

1. presence of psychosis or glucocorticoid-induced violence (as captured in the GTI specific list) always has weight=74. Disappearance of psychosis or glucocorticoid-induced violence has weight=-74.

2. minor and mild or used fully interchangeable

For the derivation from the grading to severe, moderate, minor (or mild): see table underneath:

Minor/Mild	Moderate	Severe (Specific Domain)
Insomnia – (Grade 1)	Insomnia – (Grade 2)	
Mania (Grade 1)	Mania (Grade 2)	Mania (Grade 3)
Cognitive impairment (Grade 1)	Cognitive impairment (Grade 2)	Cognitive impairment (Grade 3)
Depression (Grade 1)	Depression (Grade 2)	Depression (Grade 3)

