- The C-GTI, which serves as a primary instrument intended to capture common glucocorticoid toxicities (ie, toxicities that are likely due to glucocorticoid exposure and sensitive to cumulative doses over the period of 6 months to 3 years), has 9 functional domains (specifically: BMI, glucose control, blood pressure, lipid metabolism, bone mineral density, muscle strength, skin toxicity, neuropsychiatric effects, and infection). Each of the domains contains 3 to 4 weighted items that correspond to varying degrees of glucocorticoid toxicity within their respective domain. Among the 9 GTI domains, bone mineral density is excluded if the GTI will be measured at intervals shorter than 1 year, because bone densitometry is not sufficiently reliable in measuring changes at shorter intervals. Therefore, in the context of the ARGX-113-1904 trial with a maximum duration of 30 weeks, the index is truncated by removing the "bone mineral density" domain. Development of the GTI beyond the original validation work has suggested 2 approaches to analysis. These approaches provide complementary information about the ability of an investigational agent to reduce GC toxicity and also optimize the granularity with which the GTI captures the GC toxicity. The CWS is designed to assess cumulative GC toxicity, regardless of whether the toxicity has lasting effects or is transient. New toxicities that occur are added, but toxicities that appear to resolve on follow-up are not removed. Thus, the CWS serves as a lasting record of GC toxicity observed, and can only increase or remain the same over time. In the case of the presence of some GC toxicity at baseline, the AIS can be used to establish that a new therapy is effective at diminishing any baseline GC toxicity over time. With the AIS, toxicities can be removed if improvement occurs, and added if worsening occurs. If toxicities present at baseline or occurring during the trial resolve over the course of follow-up, then that improvement is reflected in a negative score for that item during the interval. Both the CWS and the AIS are calculated for each interval, and then the interval scores are summed.

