	No significant change	0
	Increase in skin toxicity—none to mild	8
	Increase in skin toxicity—mild to moderate	18
	Increase in skin toxicity—none to moderate	26
8. Neuropsychiatric-corticosteroid-related symptoms	Decrease in NP toxicity—moderate to none	-74
o. Rearopsychiatre concoscrotorrelated symptoms	Decrease in NP toxicity—moderate to mild	-63
	Decrease in NP toxicity—mild to none	-05
	No significant change	0
	Increase in NP toxicity—none to mild	11
		63
	Increase in NP toxicity—mild to moderate Increase in NP toxicity—none to moderate	
0. Infaction		74
9. Infection	No infection	
	Oral or vaginal candidiasis or uncomplicated zoster (<grade 3)<="" td="">19	</grade>	19
	Grade 3, 4, or 5 infection	93

Table 11:Approach to Calculating the Changes in GTI 2.0 Score: Weighted Scores
Assigned to Improvements or Worsenings in the C-GTI

BMD, bone mineral density; GTI, Glucocorticoid Toxicity Index; HgbAlc, glycated haemoglobin; LDL, low density lipoprotein; NP, neuropsychiatric.

*Bone health will not be scored as part of the C-GTI.

Table 12:GTI 2.0 Specific List: 11 Domains (9 of Which are Shared by the C-GTI) and
23 Unique Items

	At baseline or before	New since baseline
Body mass index (BMI)		
• An absolute increase in BMI of more than 8 units (and >24.9 kg/m ²)		
Blood pressure		
Hypertensive emergency (see definition, below)		
• PRES (posterior reversible encephalopathy syndrome) (see definition, below)		
Endocrine		
Symptomatic adrenal insufficiency		
Bone health		
Osteonecrosis of one joint		
Osteonecrosis of more than one joint		
• Bone mineral density decrease >6%		
Insufficiency fracture		
Insufficiency fracture in more than one bone		
Muscle and tendon		
• Severe glucocorticoid myopathy (see definition)		
• Tendon rupture		
More than 1 tendon rupture		
Eye		
Central serous retinopathy		
New-onset or worsened elevation of intraocular pressure requiring treatment or change in treatment		
Posterior subcapsular cataracts (or history of same)		
Infection		
• Grade 4 infection (see definition, below)		
Grade 5 infection (death from infection)		
Glucose tolerance		
Diabetic nephropathy		
Diabetic neuropathy		
Diabetic retinopathy		
Gastrointestinal tract		
Gastrointestinal perforation (occurring in the absence of regular nonsteroidal anti-inflammatory drug use)		
Peptic ulcer disease confirmed by endoscopy (excluding Helicobacter pylori)		
Skin		
• Severe skin toxicity (see definition, below)		
Neuropsychiatric		

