#### 4.1.2.6 OTHER EFFICACY ENDPOINTS

Other efficacy endpoints are:

1. Number of flares: count number of flares as assessed by the investigator. A new flare only emerges after a new DC. Number of flares are counted over:

- the entire study (the whole roll-over, treatment + follow-up phase)
- within each treatment period
- within each treatment period between first DC and CRmin (or end of treatment period for participants without CRmin).
- within each treatment period after CRmin.

For participants who enter the study because of a flare in the 1904 study, the initial flare (at the roll-over visit) will not be counted. Flare counts will be presented overall and by subgroup of disease status at roll-over.

2. Proportion of treatment failures as assessed by the investigator over the treatment phase. Specific reasons for treatment failure can be derived as follows in following order:

- absence of DC: if participant did not achieve DC as assessed by the investigator
- flare: if previous reason is not applicable, the reason must be a flare between DC and CRmin that is not controlled by a prednisone dose that is 2 dose levels above the dose at which the flare is observed and that is a least 0.3mg/kg qd

3. PDAI at each visit: PDAI activity subscores (mucosal, skin and scalp), PDAI activity score and PDAI total score are assessed by the investigator at each visit.

4. QoL at each visit: ABQOL (17 items) and EQ-5D-5L (i.e., mobility, self-care, usual activities, pain/discomfort, anxiety/depression and VAS) are assessed by the investigator at baseline, start of re-treatment, CRmin and Week 52/EoT/ET. A total ABQOL score is calculated as the sum of all 17 items score 0 to 3 with higher score indicating worse condition. Missing items are imputed with the average score of the present items if at least half (9) of the items are present. The total score is rounded to the highest integer.

5. C-GTI at each visit: Composite Glucocorticoid Toxicity Index comprises the Aggregate Improvement Score (AIS) and the Cumulative Worsening Score (CWS) (health impact of GC) and is measured at baseline, Week 26 and Week 52/EoT/ET. AIS and CWS are calculated for the first 26 week period (W26), for the last 26 week

SGS	Statistical Analysis Plan	
ARGX-113-1905	Final analysis	Final 1.0 of 26APR2024

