## 9. APPENDICES

#### 9.1 GTI: DERIVATION OF CWS AND AIS

#### 9.1.1 Allocate weights

Weights per item are attributed as specified below. GTI at Wx is evaluated versus previous GTI assessment. The first time point is referred to as *start (or previous)* and the second time point within each comparison is referred to as *follow-up (or current)*.

Increase, decrease or no change in medication intake compared to previous assessment are checked in the GTI assessment. A missing evaluation, including for external data, will be considered as no change with weight=0.

External GTI data (i.e. LDL/HbA1c/BP and BMI) are allocated to a GTI assessment based on dates. The last available value of these external data since previous GTI assessment will be used.

Changes from severe to moderate do not have any impact on calculation of CWS/AIS. Severe outcome on an item however is captured on the specific list (SL).

SGS	Statistical Analysis Plan	
ARGX-113-1905	Final analysis	Final 1.0 of 26APR2024

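### SAP 9.1.1.8 note 1, read literally, scores psychosis or steroid-induced violence as +74 worsening at every GTI assessment where it is present, even if unchanged since the previous one

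*SAP*

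**What the plan says.** SAP 9.1.1 sets the general rule: "GTI at Wx is evaluated versus previous GTI assessment". In SAP 9.1.1.8, a neuropsychiatric subitem with "No significant change" has weight 0. According to SAP 4.1.2.6 the C-GTI "is measured at baseline, Week 26 and Week 52/EoT/ET", so there are two scored intervals. SAP 9.1.2 then sums the interval weights over all post-baseline timepoints. The CWS takes positive weights only; the AIS takes positive and negative weights.

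Two notes stand apart from the general rule:

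- SAP 9.1.1.8 note 1: "presence of psychosis or glucocorticoid-induced violence (as captured in the GTI specific list) always has weight=74". It adds: "Disappearance of psychosis or glucocorticoid-induced violence has weight=-74".
- SAP 9.1.1.3 note 3: "Hypertensive Emergency = Y or PRES = Y at current visit is provided a score 44 regardless of the value at previous visit".

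Protocol 8.3.10 describes the CWS in terms of new events: "New toxicities that occur are added, but toxicities that appear to resolve on follow-up are not removed". It also says that a toxicity present at baseline that resolves should show as a negative AIS contribution. In Protocol Appendix 12, psychosis and violence (74 points) and hypertensive emergency and PRES (44 points) appear in Table 10, which builds the baseline score. Table 11, which scores change, has no row for any of the four. All four also sit on the GTI Specific List (Table 12), where one column is headed "New since baseline".

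**The concern.** Note 1 turns on presence, not on appearance. It carries a value that the protocol gives only for a baseline level into a score that is meant to capture change. Because the interval weights are summed, a condition that has not moved is added as fresh worsening each time it is recorded. In the AIS, the false +74 can also cancel the -74 that a later resolution earns.

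The situation is foreseeable. SAP 1.2 allows roll-over after a prednisone-related serious adverse event, and after failure to reach disease control on 1.5 mg/kg/day, so some participants may enter with steroid toxicity already present. The notes could then attribute that toxicity to the extension. The C-GTI is a named secondary endpoint, and it is the one by which the trial assesses the health impact of glucocorticoid use.

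**Working it through.** **The plan's own examples reproduce.** AIS skin example (SAP 9.1.2.2): +26 - 18 = +8. CWS neuropsychiatric example (SAP 9.1.2.1): the larger of 11 (new mild insomnia) and 74 (new moderate depression) is 74.

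**Set-up for note 1.** Let s be 1 if psychosis or violence is recorded as present and 0 if not, at roll-over, Week 26 and Week 52. The item is taken in isolation.

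- Note 1 read literally: weight +74 if s = 1 now; -74 if s was 1 and is now 0; otherwise 0.
- Change scoring (SAP 9.1.1): weight = 74 x (s now - s previous).
- CWS = sum of the positive weights. AIS = sum of all weights.

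| Roll-over, W26, W52 | Literal weights | Literal CWS/AIS | Change weights | Change CWS/AIS |
|---|---|---|---|---|
| 0, 0, 0 | 0, 0 | 0/0 | 0, 0 | 0/0 |
| 0, 0, 1 | 0, +74 | 74/74 | 0, +74 | 74/74 |
| 0, 1, 0 | +74, -74 | 74/0 | +74, -74 | 74/0 |
| 1, 0, 0 | -74, 0 | 0/-74 | -74, 0 | 0/-74 |
| 1, 0, 1 | -74, +74 | 74/0 | -74, +74 | 74/0 |
| 0, 1, 1 | +74, +74 | 148/148 | +74, 0 | 74/74 |
| 1, 1, 0 | +74, -74 | 74/0 | 0, -74 | 0/-74 |
| 1, 1, 1 | +74, +74 | 148/148 | 0, 0 | 0/0 |

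Five patterns agree. The three that differ are those in which the item is present at two consecutive assessments. The excess is 74 per such interval, so at most 2 x 74 = 148. If the item is present at roll-over and already gone by Week 26, the SAP correctly gives AIS -74.

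**Cap within the domain.** SAP 9.1.2.1 counts only the highest positive neuropsychiatric weight in an interval. If psychosis and violence fall under that rule, having both gives 74, not 148, in one interval. The CWS excess shrinks, or vanishes, when another subitem already scores +74 in that interval.

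**Note 3.** Take one hypertensive emergency between roll-over and Week 26. If Y can carry over, as it could on a form that follows the Table 12 column, it is Y at Week 26 and at Week 52: 44 + 44 = 88 instead of 44. If Y means an event since the last GTI assessment, that single event scores 44 once. A second Y is then a second event, and 88 is right.

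**Size.** SAP 1.3 gives a maximum of about 213 participants. One error of 148 moves the mean by 148/213 = 0.69, about 0.7 points. SAP 4.1.3.6 restricts the C-GTI to complete cases and SAP 2.4 repeats outputs for Japanese, Mainland Chinese and East Asian subsets. There the shift is 148/n with a smaller n, which the documents do not give.

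**The case against.** The best defence of note 1 is that it sits in a section whose heading refers to the previous assessment. Psychosis and violence carry no grade, so a weight that always applies may only mean a fixed, ungraded weight, paired with -74 on disappearance. Where the authors meant to disregard the previous visit, as in SAP 9.1.1.3 note 3, they said so. That may be the intention, but note 1 gives the weight to presence, and a programmer following it would add 74 at each assessment.

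For hypertensive emergency and PRES the defence is stronger. The protocol defines hypertensive emergency by acute organ damage and PRES as a reversible syndrome confirmed on imaging. Note 3 speaks of the value at the current and the previous visit, which suggests recording visit by visit. A repeated Y may then be a genuine new event, scored for the same reason the SAP gives for infections. A reader might infer from Table 12 that past events are in fact scored twice. The documents do not show this: the case report form is not among them, the SAP does not say which column feeds the score, and a disappearance rule makes little sense with a cumulative tick. A reader might also want a negative AIS weight once a hypertensive emergency is over. That is a design choice, and Table 11 gives no such weight.

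On impact, the objection stands. A weight of 74 is not unusual within its domain (none to moderate depression also scores 74), and the summaries involve no hypothesis test.

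**Conclusion.** The point holds for psychosis and glucocorticoid-induced violence. As written, note 1 conflicts with SAP 9.1.1 and with the protocol's definition of the CWS, and it gives a wrong score whenever the condition is present at two consecutive assessments. The excess is 74 points per such interval, up to 148, subject to the highest-subitem cap. This rests on the literal reading of the note and on the two scheduled intervals.

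For hypertensive emergency and PRES the point is conditional: there is a defect only if Y can persist from an earlier interval.

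A reader might conclude that the C-GTI results as a whole overstate steroid toxicity, or that the AIS generally misses improvement. The documents do not support that. The AIS offset is lost only when the item was still present at the assessment before it resolved. The C-GTI is tabulated overall and not by disease status at roll-over (SAP 4.1.3.7), and one maximal error is worth about 0.7 points on a mean over 213. It is a minor correction to a descriptive secondary endpoint, and it matters most for individual listings and the small regional subsets.

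**What to change.** In SAP 9.1.1.8 note 1, score +74 only when psychosis or violence is new since the previous GTI assessment, 0 when it is present and unchanged, and -74 (AIS only) when it is no longer present.

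In SAP 9.1.1.3 note 3, score +44 only for a hypertensive emergency or PRES with onset since the previous GTI assessment, checked against the adverse event start date, and state that each such event is distinct, as the SAP does for infections. No AIS reversal is needed for these acute events. Name the form field or Specific List column that supplies the four items.

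The cost is two reworded notes and a date check. Adverse event start and stop dates are already collected (SAP 5.1.1), so no new data are needed.
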